9.9. Treatment Compliance

Patients will be administered study drug in a controlled setting under the supervision of the Investigator or designee, thereby ensuring compliance with study drug administration. The Investigator or designee will ensure that all patients are adequately informed on the specific

dosing regimen required for compliance with the study protocol, ensure that the patient receives the appropriate dose at the designated time points during the study and that adequate safety monitoring occurs during the infusion ([Section 9.5](#)).

9.10. Contraception Guidance

Before receiving study drug, female patients who consider themselves to be postmenopausal must provide evidence of menopause based on a combination of amenorrhea for at least 1 year and increased serum follicle-stimulating hormone (FSH) level (> 30 IU/L) (eg, in the absence of hormone replacement therapy, dietary phytoestrogens).

Female patients of childbearing potential must use a highly effective or acceptable method of contraception (as defined below), starting at Screening and continuing for at least 8 months after the last dose of study drug.

Highly effective contraceptive methods include:

1. Hormonal contraception associated with inhibition of ovulation
2. Intrauterine device
3. Intrauterine hormone-releasing system
4. Bilateral tubal occlusion
5. Vasectomized partner, provided that the partner is the patient's sole sexual partner
6. Sexual abstinence, defined as refraining from heterosexual intercourse during the entire period of risk associated with the study drug treatment; reliability of sexual abstinence needs to be evaluated in relation to the duration of the clinical study and the preferred and usual lifestyle of the patient

Acceptable contraceptive methods include:

1. A combination of male condom with either cap, diaphragm, or sponge with spermicide (double barrier methods)

The above-listed method(s) of contraception chosen for an individual patient can be determined by the Investigator with consideration for the patient's medical history and concomitant medications.

Male patients with a female spouse/partner of childbearing potential or a pregnant or breastfeeding spouse or partner must agree to use double barrier contraception (male condom plus appropriate barrier method for the female partner) while on treatment and for at least 8 months after the last dose of study drug. Double barrier contraception is required even with documented medical assessment of surgical success of a vasectomy.

Male patients must not donate sperm while on treatment and for at least 8 months after the last dose of study drug.

10. EFFICACY ASSESSMENTS

10.1. Primary Efficacy Assessment

The primary efficacy assessment is Complete TMA Response during the 26-week Initial Evaluation Period. The criteria for Complete TMA Response are the following:

1. Normalization of platelet count
2. Normalization of LDH
3. $\geq 25\%$ improvement in serum creatinine from baseline

Patients must meet all Complete TMA Response criteria at 2 separate assessments obtained at least 4 weeks (28 days) apart, and any measurement in between, to be classified as having met the primary efficacy endpoint.

10.2. Secondary Efficacy Assessments

The following secondary efficacy assessments will be measured during the study:

1. Dialysis requirement status
2. Time to Complete TMA Response
3. Complete TMA Response status over time
4. Observed value and change from baseline in eGFR
5. CKD stage, as evaluated by eGFR at select target days and classified as improved, stable (no change), or worsened compared to baseline
6. Observed value and change from baseline in hematologic parameters (platelets, LDH, hemoglobin)
7. Increase in hemoglobin of ≥ 20 g/L from baseline, observed at 2 separate assessments obtained at least 4 weeks (28 days) apart, and any measurement in between
8. Change from baseline in QoL, as measured by EQ-5D-3L (all patients), FACIT Fatigue Version 4 (patients ≥ 18 years of age), and Pediatric FACIT Fatigue (patients < 18 years of age) questionnaires
9. TMA parameters in patients who discontinue treatment but remain in the study

11. SAFETY ASSESSMENTS

The Investigator or his/her designee will meet with patients to discuss the potential safety risks of ALXN1210 and to give the Investigator the opportunity to address any of the patient's safety concerns regarding the study.

The collection of AEs will be monitored from the time informed consent is obtained until study completion. Investigators are instructed to follow any AEs through to their conclusion (resolution or stabilization) as described in [Section 11.7.6](#). In the event of patient withdrawal from the study, AE monitoring should continue through the last patient's last study visit if possible.

The timing of the clinical and laboratory assessments to be performed is specified in the Schedule of Assessments ([Table 1](#), [Table 2](#), and [Table 3](#)). Any clinically significant abnormal results should be followed until resolution or stabilization.

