8.3.4. Replacements

If it is determined at any point that a patient's Screening data does not satisfy Inclusion Criterion number [2c](#), Exclusion Criterion number [1](#), and/or Exclusion Criterion number [2](#), after receiving at least 1 dose of investigational product (eg, patient local laboratory data used to confirm eligibility criteria are subsequently determined by a central laboratory to no longer satisfy eligibility criteria), the patient will be discontinued from the study and may be replaced. Early termination procedures will be performed on patients who are terminated early ([Section 8.3.1](#)) and all AEs will be collected until 56 days after the patient's last dose of study drug ([Section 11.7.6.1](#)).

As described in [Section 15.3](#), the Full Analysis Set (FAS) will be based on a modified intent to treat (mITT) approach, and the patients discontinued from the study for the reasons described above will be excluded from the FAS. The aim of the replacement process is to yield a FAS that includes the planned number of patients all satisfying key inclusion and exclusion criteria.

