11.7.6. Collection and Reporting of Adverse Events

11.7.6.1. All Adverse Events

All AEs (serious and nonserious) will be collected from the signing of the informed consent form (ICF) until 8 weeks (56 days) after the last dose of study drug. For patients who discontinue study drug, but remain in the study, AE data collection will continue at subsequent visits per the Schedule of Assessments, until the patient's last visit. For patients who terminate early from the study, an ET visit will be conducted as soon as possible, and a follow-up phone call will be performed 8 weeks (\pm 5 days) following the patient's last dose of the study drug. All AEs must be recorded on the eCRF upon the Investigator or his/her staff becoming aware of their occurrence.

Investigators will be instructed to report the SAE including their assessment (eg, severity, seriousness, and potential relatedness to study drug) to Alexion Global Pharmacovigilance (GPV) within 24 hours of first awareness of the event via the Safety Gateway.

If a patient's treatment is discontinued as a result of an AE, study site personnel must clearly capture the circumstances and data leading to any such dose interruption or discontinuation of treatment in the AE and Exposure pages of the eCRF.

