7.3.2. Adverse Events (AEs)

The following definitions will be used for AEs:

- Pretreatment adverse events: Any AE that starts after providing informed consent, but before the first infusion of study drug
- Treatment-emergent adverse event: Any AE that starts during or after the first infusion of study drug.
- Treatment-emergent SAE: A treatment-emergent AE (TEAE) that is serious.

PreTreatment Adverse Events will be summarized in listings and Treatment-Emergent Adverse Events will be tabulated and presented as described below.

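### For patients who withdraw, the protocol gives two different ends of AE collection, and the SAP would count any late event that is collected as treatment-emergent

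*Protocol*

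**What the plan says.** **Protocol, section 11.** The general rule is "The collection of AEs will be monitored from the time informed consent is obtained until study completion". A separate sentence asks investigators to follow AEs to resolution or stabilization and cites section 11.7.6 for that. Then, for withdrawn patients: "In the event of patient withdrawal from the study, AE monitoring should continue through the last" patient's "last study visit if possible".

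**Protocol, section 11.7.6.1.** All AEs, serious or not, "will be collected from the signing of the informed consent form (ICF) until 8 weeks (56 days) after the last dose of study drug". One group has longer collection: patients who stop the drug but stay in the study, up to their own last visit. For those who leave: "For patients who terminate early from the study, an ET visit will be conducted as soon as possible", followed by a phone call 8 weeks (± 5 days) after the last dose.

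**Protocol, section 8.3.4.** For patients removed after failing key eligibility criteria, "all AEs will be collected until 56 days after" their last dose.

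**Protocol, section 8.3.1 and the Table 3 note.** Both provide an ET visit and a call at 56 ± 5 days, with no later contact. Section 8.3.1 also has the investigator try to follow an AE that is ongoing at termination until it resolves.

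**Protocol, section 11.7.6.2.** SAEs thought to be related can be reported without time limit, and investigators may report any other SAE at any time.

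**Treatment-emergent definition.** Protocol section 15.9.1 excludes AEs that start 56 days or more after the last dose. SAP section 7.3.2 has a start but no end: "Treatment-emergent adverse event: Any AE that starts during or after the first infusion of study drug". SAP sections 5.2.1 and 9.4.6 are open-ended in the same way. SAP section 4.1 lists no changes from the protocol's analyses.

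**The concern.** The same withdrawn patient has two possible ends of AE collection: the trial-wide last visit, on a best-effort basis, or 56 days after the last dose. A site working from section 11 may keep asking about new events for years. A site working from section 11.7.6.1 makes one call and stops.

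The difference can reach the reported tables. A new non-serious event well after the 56-day call may never be collected at one site. At another it may be collected and then, under the SAP as written, counted as treatment-emergent. Protocol section 9.7 withdraws patients who receive another complement inhibitor or plasma exchange/infusion, so such an event could arise on a different therapy and still be tabulated under ALXN1210. In a single-arm study no comparator would show this.

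**Working it through.** **1. The plan's own figure.** 8 weeks × 7 = 56 days, as stated in section 11.7.6.1.

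**2. Is the section 11 milestone really trial-wide?** Sections 7.1 and 8.3.5 define the end of the trial as the last patient's last visit. Section 11 uses that milestone for withdrawn patients, and its paragraph begins with collection up to study completion. The words do not mean the withdrawn patient's own last visit.

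**3. Does any section give precedence?** Section 11 refers to 11.7.6 only for following AEs to their conclusion, not for when collection of new AEs ends. The longer collection in 11.7.6.1 covers patients who remain in the study, so it does not reach those who leave. No text ranks the two end points.

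**4. Size of the gap.** Inputs from the synopsis: first patient treated March 2017; last patient's last visit estimated for May 2023.

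Gap = (last patient's last visit) − (last dose + 56 days)

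For one dose in March 2017 followed by withdrawal:

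- 1 March 2017 + 56 days = 26 April 2017; to 31 May 2023 is 2,226 days; 2,226 / 365.25 = 6.1 years.
- 31 March 2017 + 56 days = 26 May 2017; to 1 May 2023 is 2,166 days; 2,166 / 365.25 = 5.9 years.

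The maximum is therefore 5.9 to 6.1 years, depending on the days within those months.

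**5. A late withdrawal from the same entry month.** With the last dose on Day 1807, the 56-day point is Day 1807 + 56 = Day 1863. That falls between 6 April and 6 May 2022 for a patient who started in March 2017. The gap to May 2023 is then about 1.0 to 1.15 years. A patient who enters last and receives the Day 1807 dose has no gap, because Day 1863 is also the end of the schedule.

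**6. What happens to a new event that starts after the 56-day point in a withdrawn patient**

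| Event | Under 11.7.6.1 / 8.3.4 | Under section 11 | If collected: protocol 15.9.1 | If collected: SAP 5.2.1, 7.3.2, 9.4.6 |
|---|---|---|---|---|
| Non-serious AE | Not collected | Collected if possible | Not treatment-emergent | Treatment-emergent |
| SAE judged unrelated | Not required (11.7.6.2 permits a report) | Collected if possible | Not treatment-emergent | Treatment-emergent |
| SAE thought related | Reportable without time limit (11.7.6.2) | Same | Not treatment-emergent | Treatment-emergent |

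The first two rows are where capture can differ. Protocol section 15.1 also separates data beyond 56 days after the last dose, but only for patients who stop treatment and remain in the study, so it does not settle the matter for those who withdraw.

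**The case against.** The best defence reads section 11 as best-effort follow-up of AEs already known, capped at study end. The withdrawal sentence comes straight after the one on following AEs to conclusion, it is hedged, and section 8.3.1 has a similar duty for AEs ongoing at termination. A site that makes the 56-day call and then follows open events would satisfy both. The scheduled procedures also agree with each other: ET visit, one call, nothing later.

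Part of this stands. Section 11 is not a firm requirement, and follow-up of ongoing AEs is not in conflict. But section 11 already covers follow-up to conclusion in its own sentence, the withdrawal sentence is not limited to ongoing events, and the paragraph speaks of collection to study completion. The hedge leaves the extent of effort to each site, which makes uneven capture more likely.

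Several stronger readings are tempting but not supported:

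- *Deaths and serious events would be lost.* Section 11.7.6.2 keeps related SAEs reportable indefinitely and allows any other SAE to be reported at any time.
- *The affected patients are those who leave for AEs or lack of effect.* Section 8.3.1 lists neither as a termination criterion, although such patients could leave through consent withdrawal, the best-interest clause or prohibited therapy. Section 8.3.2 lets patients who stop the drug stay in the study.
- *About 5 or 6 patients are affected (10% of 55 = 5.5).* The 10% is a planning allowance for evaluability by Day 183, not a whole-study withdrawal rate.
- *Each late event moves a rate by 1/55 = 1.8 percentage points.* This holds only with 55 treated patients and no earlier event in that category, since SAP section 7.3.2.2 counts a patient once per class and term.
- *Capture does differ between sites.* The documents show only that it can.

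It is also fair to say that this is an estimation study with no between-arm comparison, and that the primary endpoint is untouched.

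**Conclusion.** The inconsistency is real: wrong as written. Section 11 and the 56-day sections set different ends for collecting new AEs in withdrawn patients, and nothing resolves the difference. It concerns new late non-serious AEs and SAEs judged unrelated. The six-year figure is a worst case that rests on immediate withdrawal in March 2017 and on the estimated last visit in May 2023; later withdrawal or later entry shortens it. How many patients or events are involved cannot be derived from the documents.

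The protocol's own treatment-emergent limit would keep late events out of the incidence tables, but the SAP omits it without declaring a change. Adding it to the SAP would protect the treatment-emergent tables. It would not make collection even, nor the listings of all AEs (SAP section 7.3.2.1), so both documents need correcting.

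**What to change.** 1. **Protocol.** Reconcile section 11 with sections 8.3.1, 8.3.4 and 11.7.6.1 so that one end of collection for new AEs in withdrawn patients applies at all sites. The low-cost route is to align the section 11 sentence with the 56-day sections. Keep the section 8.3.1 follow-up of AEs ongoing at termination and the section 11.7.6.2 provision for related SAEs.
2. **SAP.** Add the 56-day limit of protocol section 15.9.1 to the treatment-emergent definition in section 7.3.2, and carry it through to sections 5.2.1 and 9.4.6, so that the AE tables count only events inside the window.

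Cost: one protocol sentence at the next amendment, one SAP sentence and a note to sites, with no new visits. The downside is that some late events in withdrawn patients would no longer be sought. The opposite route, extending the other sections to study end, would also remove the contradiction, but it would require years of added contact with patients who have left and is not a small change.

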11.1. Demographic/Medical History

11.1.1. Demographics and Baseline Characteristics

A review of demographic parameters, including age, gender, race, and ethnicity will be performed. A complete medical history will be taken and documented. Weight and height will be recorded. Height will be measured at Screening only.

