6.2.2. Secondary Efficacy Endpoints

The secondary efficacy endpoints of the study are the following and will be measured through 26 weeks and over the entire study period:

1. Dialysis requirement status
2. Time to Complete TMA Response
3. Complete TMA Response status over time
4. Observed value and change from baseline in eGFR
5. CKD stage, as evaluated by eGFR at select target days and classified as improved, stable (no change), or worsened compared to baseline
6. Observed value and change from baseline in hematologic parameters (platelets, LDH, hemoglobin)
7. Increase in hemoglobin of ≥ 20 g/L from baseline, observed at 2 separate assessments obtained at least 4 weeks (28 days) apart, and any measurement in between
8. Change from baseline in QoL, as measured by EQ-5D-3L (all patients), FACIT Fatigue version 4 (patients ≥ 18 years of age), and Pediatric FACIT Fatigue (patients < 18 years of age) questionnaires
9. TMA parameters in patients who discontinue treatment but remain in the study

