7.1. Summary of Study Design

Study ALXN1210-aHUS-311 is a Phase 3, open-label, single arm, multicenter study to evaluate the safety and efficacy of ALXN1210 administered by intravenous (IV) infusion to adolescent (12 to < 18 years of age) and adult (≥ 18 years of age) patients with aHUS. The study will enroll approximately 55 patients to receive ALXN1210. All patients must be naïve to complement inhibitor treatment and include at least 6 and up to 10 adolescent (12 to < 18 years of age at Screening) patients and at least 10 and up to 25 patients with prior kidney transplants. A minimum of 30 patients who meet all laboratory criteria for TMA (platelet count of < 150,000 per microliter, LDH $\geq 1.5 \times$ upper limit of normal (ULN), hemoglobin \leq lower limit of normal (LLN), and serum creatinine level \geq ULN) as determined by the central laboratory at Day 1, will be enrolled.

The study consists of an up to 7 day Screening Period, a 26-week Initial Evaluation Period, and an Extension Period until the product is registered or approved (in accordance with country-specific regulations) or for up to 4.5 years, whichever occurs first. Dosages are based on the patient's body weight recorded at the last visit or more recently (Table 6). Patients will receive a loading dose of ALXN1210 IV (2400 mg for patients weighing ≥ 40 to < 60 kg, 2700 mg for patients weighing ≥ 60 to < 100 kg, 3000 mg for patients weighing ≥ 100 kg) on Day 1, followed by maintenance doses of ALXN1210 IV (3000 mg for patients weighing ≥ 40 to < 60 kg, 3300 mg for patients weighing ≥ 60 to < 100 kg, 3600 mg for patients weighing ≥ 100 kg) on Day 15 and once every 8 weeks (q8w) thereafter for a total of 26 weeks of treatment in the Initial Evaluation Period followed by maintenance doses q8w in the Extension Period (Figure 1). The end of trial is defined as the last patient's last visit.

Figure 1 illustrates the study design.

Figure 1: Study Design Schematic for Clinical Protocol ALXN1210-aHUS-311

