- ^l A predose serum sample will be collected on Days 351, 575, 743, and Day 911. For patients who discontinue treatment but remain in the study, ADA sample will be collected at any time during the visits until approximately 39 weeks after the last dose of ALXN1210. In case of retreatment, if the patient starts the retreatment on a scheduled visit which does not include ADA sample collection, a predose ADA sample must be collected. If a supplemental dose is administered, a predose ADA sample will be collected. All collection times will be recorded in the eCRF.
- ^m Review the Clinical Trial Participant Safety Information Card with the patient and discuss the importance of carrying the safety card at all times, and the risks ALXN1210 treatment, including the risk of meningococcal infection.
- ⁿ Concomitant medications must be collected at all study visits (and at the 56 [± 5]-day follow-up phone call for patients who terminate the study early) and checked against the prohibited medication listed in [Section 9.7](#).
- ^o Extension Period begins at the start of Day 183 dosing. The dose of ALXN1210 is based on the patient's body weight recorded at the last visit or more recently. For patients who discontinue ALXN1210 treatment, remain in the study, and further receive retreatment, the dosing details are provided in [Section 8.3.2.1](#).

Table 3: Schedule of Study Visits and Assessments: Extension Period Day 967 to Day 1863

Period	Extension Period																
	967	1023	1079	1135	1191	1247	1303	1359	1415	1471	1527	1583	1639	1695	1751	1807	1863/ ET/EOS
Study Day	±7	±7	±7	±7	±7	±7	±7	±7	±7	±7	±7	±7	±7	±7	±7	±7	±7
Window (day)	±7	±7	±7	±7	±7	±7	±7	±7	±7	±7	±7	±7	±7	±7	±7	±7	±7
Weight	X	X	X	X	X	X	X	X	X	X	X	X	X	X	X	X	X
Pregnancy test ^a	X	X	X	X	X	X	X	X	X	X	X	X	X	X	X	X	X
FACIT-Fatigue questionnaire /Pediatric FACIT-Fatigue questionnaire ^{b,c}				X				X				X				X	X
EQ-5D-3L questionnaire ^c				X				X				X				X	X
Physical examination																	X
Abbreviated physical examination ^d	X	X	X	X	X	X	X	X	X	X	X	X	X	X	X	X	X
Assessment of extra-renal signs or symptoms of aHUS				X				X				X				X	X
Vital signs ^e	X	X	X	X	X	X	X	X	X	X	X	X	X	X	X	X	X
Safety 12-Lead ECG ^f																	X
Chemistry	X	X	X	X	X	X	X	X	X	X	X	X	X	X	X	X	X
LDH isozymes ^g	X	X	X	X	X	X	X	X	X	X	X	X	X	X	X	X	X
Hematology and coagulation ^h	X	X	X	X	X	X	X	X	X	X	X	X	X	X	X	X	X
Urinalysis and urine chemistry	X	X	X	X	X	X	X	X	X	X	X	X	X	X	X	X	X
PK/PD sampling ⁱ			X ⁱ			X ⁱ			X ⁱ				X ⁱ			X ⁱ	X ⁱ

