11.4.3. Serum Chemistry

Blood samples will be analyzed for the serum chemistry parameters listed in [Appendix D](#). Indirect bilirubin is calculated from total and direct bilirubin values; therefore, indirect bilirubin results will not be available if direct bilirubin is below the limit of quantification.

Serum FSH level will be measured during Screening for postmenopausal female patients to confirm their postmenopausal status.

Chemistry assessments will be performed at the time points specified in the Schedule of Assessments ([Table 1](#), [Table 2](#), and [Table 3](#)). The eGFR will be calculated for all visits at which serum chemistries are collected using the Modification of Diet in Renal Disease formula in patients ≥ 18 years of age and Schwartz formula in patients < 18 years of age.

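### Height is recorded only at Screening, so Schwartz eGFR in adolescents who are still growing is understated in the Extension Period; the effect is small and confined to 6 to 10 patients

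*Protocol*

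**What the plan says.** Protocol 11.1.1: "Height will be measured at Screening only". The schedules in Protocol 7.3 match this. Table 1 has the only height row, with one entry in the Screening column. Tables 2 and 3 have a weight row and no height row.

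Protocol 11.4.3: "The eGFR will be calculated for all visits at which serum chemistries are collected". The method is MDRD for adults and the "Schwartz formula in patients < 18 years of age". Tables 1 to 3 schedule chemistry up to the last visit; the last table is titled "Extension Period Day 967 to Day 1863".

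Protocol 7.1 plans "at least 6 and up to 10 adolescent (12 to < 18 years of age at Screening) patients" among about 55 in total. The Extension Period lasts until registration or approval "or for up to 4.5 years, whichever occurs first".

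eGFR value and change are secondary endpoints, as is "CKD stage, as evaluated by eGFR at select target days and classified as improved, stable (no change), or worsened compared to baseline" (Protocol 10.2). Under Protocol 6.2.2 the secondary endpoints "will be measured through 26 weeks and over the entire study period".

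SAP 9.4.9, which covers creatinine and eGFR, deals only with dialysis. Neither document supplies a later height, says which height enters Schwartz, or says whether age at Screening or age at the visit selects the formula. SAP 7.1.3.1 lists height at first infusion as a demographic variable, although no height is scheduled on Day 1.

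**The concern.** A patient can enter at 12 and be followed for years with eGFR computed at each visit. If the formula uses height, the only height on file becomes too small as the patient grows. Computed eGFR then falls below the value that the current height would give, and the gap widens with growth. A kidney whose function is stable could be listed as losing eGFR or, near a cut-point, as having worsened in CKD stage. The affected outputs are the long-term eGFR and CKD-stage summaries. Analysts could not reliably repair them later, because the heights would not have been collected.

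**Working it through.** **Inputs from the documents.** Height at Screening only (Protocol 11.1.1, Tables 1 to 3); eGFR at all chemistry visits (Protocol 11.4.3); 6 to 10 adolescents of about 55 (Protocol 7.1); last visit Day 1863 (Protocol Table 3); CKD cut-points 15, 30, 45, 60 and 90 mL/min/1.73 m² (Protocol Appendix J).

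**Assumptions, not in the documents.** Schwartz eGFR = k × height / serum creatinine. Growth is given as a range, because neither document contains growth data.

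**1. Length of follow-up.** (1863 − 1) / 365.25 = 5.10 years. From the text, 182 / 365.25 + 4.5 = 5.00 years. The two agree within 2%, so about five years is correct as a maximum.

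**2. Bias.** With H0 the Screening height and Ht the current height, computed eGFR / eGFR with current height = H0 / Ht. The constant k and the creatinine cancel.

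- Proportional growth of 5, 10 or 15%: 1 − 1/1.05 = 4.8%; 1 − 1/1.10 = 9.1%; 1 − 1/1.15 = 13.0% understatement.
- From H0 = 150 cm: 3 cm (taken as 26 weeks) gives 150/153 − 1 = −2.0%; 10 cm gives 150/160 − 1 = −6.2%; 20 cm gives 150/170 − 1 = −11.8%; 25 cm gives 150/175 − 1 = −14.3%.
- Over H0 of 140 to 170 cm and growth of 10 to 25 cm, the range is −5.6% (170/180) to −15.2% (140/165).
- No further growth: 0%.

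**3. CKD stage.** A patient is put one stage too severe when eGFR with current height lies between a cut-point c and c × Ht/H0.

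| Growth from 150 cm | Bands recorded one stage too severe |
|---|---|
| 3 cm | 15–15.3, 30–30.6, 45–45.9, 60–61.2, 90–91.8 |
| 20 cm | 15–17, 30–34, 45–51, 60–68, 90–102 |

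For example, with 20 cm of growth a constant 62 is recorded as 62 × 150/170 = 54.7 (stage 2 to 3a), and a constant 95 as 83.8 (stage 1 to 2). Outside these bands the stage is unchanged.

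**4. Pooled mean.** Adolescents are 6/55 = 10.9% to 10/55 = 18.2% of the sample. If every one carried the 20 cm bias (20/170 = 11.76%) and had eGFR similar to the adults, the mean would shift by 6/55 × 11.76% = 1.3% to 10/55 × 11.76% = 2.1%.

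**5. Who stays on Schwartz.** If age at Screening selects the formula, all adolescents remain on it to Day 1863. If age at the visit selects it, only those younger than 18 − 5.10 = 12.9 years at entry do.

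**The case against.** The case against giving this weight is substantial, and most of it stands.

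- **The size rests on outside assumptions.** The documents name Schwartz without printing it and give no growth data. The direction follows from the assumed form; the magnitude is only a range.
- **The planned outputs are little affected.** The primary endpoint's renal component is serum creatinine (Protocol 10.1, SAP 5.1.1). No formal test is planned (SAP 7.2.1.4). The report carrying the primary endpoint is at 26 weeks (SAP 4.3), where the bias is about 2% under the assumed growth. eGFR is summarized overall, by transplant status and on the per protocol set (SAP 7.2.2.4), with no adolescent table, so the bias is diluted. During dialysis eGFR is set to 10 whatever the height.
- **Follow-up may be shorter.** Approval can end the Extension Period early. SAP 4 and 4.3 describe a two-year Extension, which would end near Day 911, or (911 − 1)/365.25 = 2.5 years. The Protocol does schedule visits to Day 1863 and plans a final report at study completion, so longer exposure remains possible.
- **The error is conservative.** It understates renal recovery. That is true, but it still distorts a long-term endpoint.

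A reader might also infer that adolescents show an artificial decline followed by an abrupt jump at 18, when MDRD replaces Schwartz. The documents do not support this, because they do not say which age selects the formula. For the fatigue questionnaires the schedule footnotes fix age at Screening; for eGFR nothing is said. If Screening age governs, there is no switch. If age at the visit governs, only the youngest entrants could accumulate the full five-year bias, and a change of formula could cause a discontinuity even with current heights.

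**Conclusion.** The point holds as a minor design gap in the long-term data. As written, the plan gives a biased Extension Period eGFR in any adolescent who grows after Screening, by the factor Screening height / current height. CKD stage can be recorded too severely only near a cut-point. The understatement is relative to eGFR with current height, so observed eGFR may still rise with recovery. It should not be read as a general downward drift in adolescents: it is zero once growth stops, reaches 6 to 10 patients at most, and has limited effect on the pooled mean. No jump at 18 is claimed. The conclusion rests on Schwartz being proportional to height over creatinine; the sizes rest on the assumed growth and, for the pooled figure, on adolescents having eGFR similar to the adults.

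**What to change.** For patients under 18 at Screening, record height at least yearly, at Extension visits already scheduled, for as long as Schwartz is applied. Amend Protocol 11.1.1 and add a height row to Tables 2 and 3. A yearly reading leaves a small residual: for an assumed 5 cm of growth from 150 cm since the last reading, 150/155 − 1 = −3.2%. A reading at every eGFR visit would remove the height-related bias, but slow growth hardly requires it.

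In SAP 9.4.9, state that Schwartz eGFR uses the most recent recorded height, and whether age at Screening or age at the visit selects the formula. The height reading alone does not settle the second question.

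The cost is one extra height reading at visits where weight is already taken, and one eCRF field, for 6 to 10 patients.
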